2.4 Correlative Studies

Additional details and methods are provided in [Appendix II](#), [Appendix IX](#), and [Appendix X](#).

2.4.1 Assessment of the effect of nelfinavir on KSHV lytic gene expression in tumor tissue.

As described in [Section 2.1](#), KSHV lytic gene expression may contribute to tumor development and progression. We hypothesize that nelfinavir will decrease lytic gene expression in tumors. This will be ascertained by whole genome mRNA profiling at the AMC Genomics Core and immunohistochemistry (IHC) on a subset of viral proteins at the AMC Pathology Core Laboratory.

2.4.2 Correlation of nelfinavir and the primary active metabolite, M8, concentrations with tumor response, antiviral response, and adverse effects in participants with KS.

The pharmacokinetics (PK) of nelfinavir are non-linear and show considerable inter-patient variability. We hypothesize that higher drug levels will be associated with tumor response, as well as lower levels of viral lytic gene expression in tumors ([Section 2.4.1](#)) and KSHV copy number in saliva, PBMC, and plasma ([Sections 2.4.3](#) and [2.4.4](#)). Because nelfinavir is metabolized by CYP3A and CYP2C19, genotyping will be performed to identify predictors of nelfinavir levels and response to treatment. Nelfinavir/M8 concentrations will be performed at the AMC Pharmacology Core Lab at Johns Hopkins University and genotyping will be performed at the AMC Genomics Core by targeted sequencing.

2.4.3 Assessment of the effect of nelfinavir on KSHV copy number in saliva.

KSHV lytic replication is common in the oropharynx¹⁵ and decreases with active antiviral treatment²⁴. As such, KSHV copy number will be measured in saliva using quantitative polymerase chain reaction (qPCR) as a convenient estimate of antiviral activity. KSHV qPCR will be conducted at the AMC Genomics Core Laboratory.

2.4.4 Exploratory: Assessment of the effect of nelfinavir on KSHV and EBV copy number in PBMC and plasma; and HSV, CMV, and EBV viral load in saliva.

KSHV replication in blood may be a more relevant predictor of response to nelfinavir than oral replication. As such, qPCR may be used to measure KSHV in stored PBMC and plasma from participants. EBV viral load will also be evaluated in these samples.

Additionally, HSV, CMV, and EBV viral load will be assessed in saliva at the AMC Virology Core. KSHV qPCR for plasma and PBMC viral load will be performed at the AMC Virology Core.

PBMC/Plasma viremia: Because KSHV can reactivate sporadically, and viremia is not always persistent in persons with KS (present on median of 20% of days in endemic KS and on 67% of days in HIV-associated KS in Uganda¹ the more

samples obtained, the more stability and precision in estimates. Therefore, we would like to obtain 2 samples pre-treatment and 8 samples on treatment. The timing of those samples is not important in a Poisson mixed effects model, so we are basing the timing on feasibility. For example, 2 samples can be achieved through weekly sampling during the 4 weeks pre-treatment. Eight samples on treatment can be obtained twice monthly in order to coordinate the blood draw schedule with clinical/tumor assessment visits and safety lab blood draws, which will also occur on this schedule (safety labs monthly but coordinated with bi-weekly visits); this will reduce burden on participant and maximize study resources. Effect of the study drug on KSHV replication is an important outcome of this study.

3.0 PARTICIPANT SELECTION

A rostered AMC investigator (CTEP-registered physician investigator) must document that each protocol participant meets all stated eligibility criteria. Participating sites must have documentation that each eligibility requirement is satisfied prior to participant enrollment. In compliance with CTEP policy, no exceptions to eligibility criteria will be granted under any circumstance.

NOTE: Institutions may use this section of the protocol as an eligibility checklist for source documentation if it has been reviewed, signed, and dated before registration/randomization by the study investigator. If used as source documentation, this checklist must be printed, the investigator must check each item to document their assessment that the participant meets each eligibility criterion, and the completed checklist must be maintained in the participant's chart.

Participant ID Number: 098 - _____ - _____

Patient's Initials (F, M (optional), L): _____

3.1 Eligibility Criteria

- 3.1.1 Biopsy-proven KS involving skin (with or without visceral involvement) without need for urgent cytotoxic therapy. There should be no evidence of improvement in KS in the 4 weeks immediately prior to study enrollment and treatment.
- 3.1.2 Known HIV-1 infection status, as documented by any nationally approved, licensed HIV rapid test performed in conjunction with screening (or enzyme-linked immunosorbent assay [ELISA] test kit) and confirmed by an approved test at each study site¹.

U.S. participants only: Alternatively, this documentation may include a record demonstrating that another physician has documented the participant's HIV status based on either:

1. Approved diagnostic tests, or
2. The referring physician's written record that HIV infection was documented, with supporting information on the participant's relevant medical history and/or current management of HIV infection.

Participants enrolled outside the U.S. must have a confirmatory diagnostic test sequence as appropriate per national standards, detailed as above, performed regardless of prior documented HIV status.

¹ NOTE: The term "licensed" refers to a U.S. FDA-approved kit or for sites located in countries other than the United States, a kit that has been certified or licensed by an oversight body within that country and validated internally.

WHO (World Health Organization) and CDC (Centers for Disease Control and Prevention) guidelines mandate that confirmation of the initial test result must use a test that is different from the one used for the initial assessment. A reactive initial rapid test should be confirmed by either another type of rapid assay or an E/CIA that is based on a different antigen preparation and/or different test principle (e.g., indirect versus competitive), or a Western blot or a plasma HIV-1 RNA viral load.

For HIV-negative participants, a negative result must be documented by any one of the nationally approved or licensed tests, including rapid tests, and must be performed no more than 4 weeks before enrolling to the treatment segment

- 3.1.3 Participant may be either previously untreated for KS or refractory to or intolerant of any one or more prior KS therapies.
- 3.1.4 Age \geq 18 years. Because no dosing or adverse event data are currently available on the use of high dose nelfinavir in participants $<$ 18 years of age, children are excluded from this study.
- 3.1.5 ECOG performance status \leq 2 (Karnofsky \geq 50%, see [Appendix III](#)).
- 3.1.6 Life expectancy of greater than 3 months as assessed by the investigator.
- 3.1.7 Participants must have organ and marrow function within the following parameters (within 4 weeks before enrolling for study treatment):
 - Leukocytes: \geq 3,000/mm³
 - Absolute neutrophil count: \geq 1,500/mm³
 - Platelets: \geq 100,000/mm³
 - Total bilirubin: within normal limits at each study site local laboratory
 - AST (SGOT) / ALT (SGPT): \leq 2.5 X institutional upper limit of normal (ULN)
 - Creatinine:
 - Creatinine levels \leq upper limit of institutional normal; or
 - Creatinine clearance \geq 60 mL/min/1.73 m² for participants with serum creatinine levels above institutional normal.
- 3.1.8 HIV seropositive participants must be on ART with the following criteria:
 - A complete ART regimen that adheres to the current DHHS Guidelines for the Use of Antiretroviral Agents in Adults and Adolescents Living with HIV (<https://aidsinfo.nih.gov/guidelines/html/1/adult-and-adolescent-arv/0>) or any co-formulated combination that is FDA approved for the treatment of HIV. See [Section 3.2.5](#) for details regarding eligible antiretroviral drugs.
 - The ART regimen must not include PIs (including nelfinavir); participants must not have received a PI-based regimen for at least 4 weeks prior to study enrollment.
 - Modification of ART regimen limited to eligible antiretroviral drugs while on study is allowable.
 - Participants must either have an undetectable HIV plasma RNA, or if plasma RNA detectable, it must be decreasing while on the same stable regimen for a minimum of 12 weeks prior to study enrollment.
 - No evidence of incomplete virologic response or virologic failure (two consecutive HIV RNA levels \geq 200 copies/mL after 24 weeks on a stable regimen or after achieving an undetectable viral load) within 12 weeks before

study enrollment.

- 3.1.9 The effects of high dose nelfinavir on the developing human fetus are unknown. For this reason, women of child-bearing potential must agree to use adequate contraception (barrier or other non-hormonal method of birth control, or abstinence) prior to study enrollment and for the duration of study participation. Hormonal contraception alone is contraindicated for pregnancy prevention in this study due to potential loss of efficacy from drug interactions with nelfinavir. Should a woman become pregnant or suspect she is pregnant while she is participating in this study, she should inform her treating physician immediately.
- 3.1.10 Ability to understand and the willingness to sign a written informed consent document.

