Proposals to evaluate the effects of nelfinavir on KSHV infection and KS in HIV-infected individuals have focused on the potential confounding by the antiretroviral activity of nelfinavir; even with adjustment for HIV viral load and CD4 counts, any effect of nelfinavir might still be due to enhanced control of HIV infection. By including participants with KS but without HIV, we have the ability to definitively examine the direct clinical antitumor and antiviral effects of nelfinavir, which may provide valuable clinical information regarding the treatment of KS in HIV-negative individuals, as well as those who are HIV-infected. Additionally, because all prior studies in reducing incident KS or treating KS with PIs have focused on ART-naïve persons, it is difficult to compare studies of persons receiving modern highly-active ART regimens, that do or do not include PIs, directly for their effects on KS and KSHV, because it is known that PIs provide more rapid virologic and immunologic responses than triple nucleoside/nucleotide reverse transcriptase inhibitor (NRTI) regimens or non-nucleoside reverse transcriptase inhibitor (NNRTI) regimens (unclear vs. recently utilized integrase inhibitors). Therefore, in this study, we propose to add nelfinavir to stable complete ART regimens in HIV-infected persons and in HIV-negative KS participants, in order to remove the HIV virologic and immunologic confounding implied in PI use. This is distinct from modern trials, which evaluate cytotoxic chemotherapy plus ART-initiation in previously ART-naïve persons. Thus, we expect we

may see less robust responses in persons with stable disease (SD) despite ongoing ART usage⁵⁸⁻⁶⁰. Comparable trials of novel agents, such as valproic acid or VEGF inhibitors in persons already on stable ART at enrollment, showed much smaller effect sizes between 20-30%⁶¹⁻⁶⁴.

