10.0 STATISTICAL CONSIDERATIONS

10.1 Study Design/Endpoints

Currently approved cytotoxic chemotherapy regimens result in a roughly 40% partial or complete response (total response) rate in persons who are not ART-naïve (who initiate ART and chemotherapy concurrently). Our hypothesis is that the dose-escalation regimen will result in at least a 20% improvement in PR or CR above the historically defined rate of spontaneous KS regression, which is 20%. We chose to evaluate a 20% improvement in total response rate because we felt that this would be both a clinically significant improvement and at least equivalent to current chemotherapy. Because NFV has many fewer toxicities and requires less monitoring, oral administration, and less cost and potential for better access compared to chemotherapy, a finding of at least equivalence could be considered an improvement over the standard-of-care. Because the cost and feasibility of using an all-oral NFV regimen in resource-limited settings would provide a significant implementation and access benefit over cytotoxic chemotherapy, we feel strongly that NFV should be proven similarly efficacious to current chemotherapy, rather than superior to it. Therefore, we have chosen a design with 90% power at a one-sided 10% significance level to test the hypothesis that 40% of participants receiving NFV at standard followed by high-dosing regimens will be able to attain PR or CR. The null hypothesis is that we will fail to detect a response superior to the rate of spontaneous tumor regression (20%). Participants from both the international and domestic protocol will contribute to the single analysis plan, which is based on HIV status and not site of recruitment.

Primary objective

To determine the efficacy of a therapeutic escalation strategy consisting of standard dose nelfinavir, followed by high dose nelfinavir, for the treatment of Kaposi sarcoma (KS) tumor lesions. The binomial proportion and its exact 95% confidence interval will be used to estimate the response rate in the study. With 36 evaluable participants, the null hypothesis will be rejected if 11 or more participants respond. Response rates will be estimated using the binomial proportion and its exact 95% confidence interval separately for HIV positive and HIV negative participants.

Secondary objectives

- To evaluate the safety of high dose nelfinavir among participants with KS.

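### The 12-week stable-ART requirement in section 3.1.8 covers only participants with detectable HIV RNA, so a recent ART starter who is already undetectable can enrol and an ART-driven response could be credited to nelfinavir

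*Combined protocol and SAP*

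**What the plan says.** **Intent.** Section 2.3 (Study Design and Rationale) states: "we propose to add nelfinavir to stable complete ART regimens in HIV-infected persons". It contrasts this with trials that start ART and chemotherapy together in ART-naïve persons. It expects weaker responses in participants whose KS is stable despite ongoing ART.

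**Eligibility.** Section 3.1.8 lists the ART conditions for HIV-positive participants:

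- Viral load: "Participants must either have an undetectable HIV plasma RNA, or if plasma RNA detectable, it must be decreasing while on the same stable regimen", followed directly by "for a minimum of 12 weeks prior to study enrollment".
- Virologic failure: "No evidence of incomplete virologic response or virologic failure" within 12 weeks before enrollment.
- Protease inhibitors: "participants must not have received a PI-based regimen for at least 4 weeks prior to study enrollment".
- Changes on study: "Modification of ART regimen limited to eligible antiretroviral drugs while on study is allowable".

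Section 3.1.1 adds, for all participants: "There should be no evidence of improvement in KS in the 4 weeks immediately prior to study enrollment and treatment".

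**Analysis.** Section 10.1 frames the target as an improvement "above the historically defined rate of spontaneous KS regression, which is 20" (percent). The null hypothesis is rejected if 11 or more of 36 evaluable participants respond, with HIV-positive and HIV-negative participants pooled. Response rates with exact 95% confidence intervals are also planned separately by HIV status. No analysis takes time on ART into account.

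**The concern.** The viral-load condition is an either/or. The 12 weeks on an unchanged regimen qualifies the second limb, detectable and falling RNA. The first limb, undetectable RNA, carries no duration. Section 3.0 allows no eligibility exceptions and lets sites use the criteria as a signed checklist, so the literal wording is what sites will apply.

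A participant who began ART less than 12 weeks ago and is already suppressed therefore qualifies. If that participant's KS then regresses because of ART, the trial has no control arm and no adjustment that would separate this from a nelfinavir effect. The event counts toward the 11 responders and toward the HIV-positive response rate. The fixed 20% comparator is described as a spontaneous regression rate. Nothing in the plan says that it allows for participants newly on ART.

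**Working it through.** **Step 1. Does any other criterion close the gap?** Take a suppressed participant who started ART recently.

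| Criterion | Effect on this participant |
|---|---|
| 3.1.8, viral load | Satisfied by the undetectable limb; no duration |
| 3.1.8, virologic failure | Excludes failure only; sets no minimum time on ART |
| 3.1.8, PI washout | Concerns prior PI use; sets no minimum time on ART |
| 3.1.1, no KS improvement for 4 weeks | Excludes regression already under way; does not reach regression that starts later |

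Section 4.1 allows up to 8 weeks at the standard dose plus up to 16 at the high dose, 8 + 16 = 24 weeks. Regression beginning in that time is assessed as response. The gap stays open.

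**Step 2. Reproduce the stated design.** Inputs from sections 10.1 and 10.2: N = 36, reject at 11 or more, null rate 0.20, alternative 0.40, one-sided level 0.10, power 0.90.

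- P(X ≥ 11) for X ~ Bin(36, 0.20) = 0.0889, within the 0.10 level.
- P(X ≥ 11) for X ~ Bin(36, 0.40) = 0.9096, above 0.90.

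The design is correct as stated. The issue is who enters it.

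**Step 3. Illustrate the effect.** Suppose nelfinavir does nothing. Let k of the 36 be recent ART starters who respond to ART alone with probability q, and let the other 36 − k respond at 0.20. Then X = A + B with A ~ Bin(36 − k, 0.20) and B ~ Bin(k, q), independent, and the false-positive probability is P(A + B ≥ 11). **Both k and q are assumptions; the documents give neither.**

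| k | q = 0.30 | q = 0.40 | q = 0.50 | q = 0.60 |
|---|---|---|---|---|
| 3 | 0.111 | 0.136 | 0.163 | 0.193 |
| 6 | 0.137 | 0.197 | 0.268 | 0.350 |

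The average response rate moves little. At the mildest corner it is (33 × 0.20 + 3 × 0.30)/36 = 7.5/36 = 0.208. At the most severe it is (30 × 0.20 + 6 × 0.60)/36 = 9.6/36 = 0.267. The tail probability is sensitive to such shifts because the cut-off lies close to the null: 11/36 = 0.306 against 0.20. With k = 0 or q = 0.20 the probability stays at 0.089.

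**The case against.** The strongest reply has four parts.

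1. **The purpose stated in section 2.3 is narrower than a reader might infer.** It is tempting to say that recent-ART regression is exactly the confounding the section claims to remove. The text speaks of HIV-related confounding that comes with PI use, and its main worry is nelfinavir's own antiretroviral activity. An already suppressed participant leaves little HIV replication for nelfinavir to act on, so an undetectable limb without a duration serves that purpose. This stands. What remains is the mismatch with the section's own description of stable ART and its contrast with ART-initiation trials.

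2. **Section 3.1.1 is a real guard.** A recent starter must be suppressed and must also show no KS improvement for 4 weeks. A reader might infer that this criterion has no earlier measurement behind it, because the photographic tumor assessment falls within 7 days of first dose (8.1.3). That goes too far: section 8.1 also schedules a physical examination, KS signs and symptoms, and KS staging within 4 weeks before enrollment. The guard does select against ART responders, and the q values above make no allowance for that. It still cannot act on regression that begins after entry.

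3. **Switching regimens is a different matter.** The wording also admits suppressed participants who changed regimen recently, and a reader might infer that their KS would regress too. The documents give no reason to expect regression after a switch in someone already suppressed. The concern is limited to recent starters.

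4. **The plan already has partial protection.** HIV-negative participants are unaffected, and rates are reported by HIV status. Section 4.2 requires concurrent drugs and ART changes to be captured. These help interpretation but do not protect the pooled 11-of-36 decision. The sponsor may also have meant the 12 weeks to cover both limbs, but the sentence does not say so.

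**Conclusion.** The concern holds as a gap between an eligibility sentence and the design it is meant to deliver. As written, section 3.1.8 sets no minimum time on ART for an undetectable participant, and the pooled test would count any later ART-driven regression as nelfinavir response. This rests on the text alone and is firm.

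The effect on the primary test is much less certain. A reader might infer that the HIV-positive estimate is biased upward or that the primary test is invalid. The documents support neither statement: bias arises only if such participants enrol, and only if they respond to ART more often than 20% after passing section 3.1.1. A new starter must also reach undetectable RNA first, which narrows the route. The range of 0.11 to 0.35, against 0.089 with no such participants, shows what 3 or 6 of the planned 18 HIV-positive participants could do at response rates of 30% to 60%. It is not an estimate. The point is worth fixing because the repair is cheap, not because harm has been shown.

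**What to change.** - **Reword section 3.1.8** so that the existing 12-week period on the same complete ART regimen applies to every HIV-positive participant, with HIV RNA either undetectable, or detectable and decreasing. No new viral-load limit is needed for this point.
- **Record** the ART start date and the date of the last regimen change before enrollment. Section 4.2 captures concurrent drugs and on-study ART changes but does not ask for these dates specifically.
- **Add a supportive analysis:** pooled and HIV-positive response rates with exact 95% confidence intervals, with and without participants who recently started ART. Define the cut-off before the response data are examined. For anyone enrolled under the present wording, 12 weeks is the natural choice because it is the sponsor's own period. The 11-of-36 rule stays with the full set.

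The sample size of 36, the rejection rule, the level and the power do not change. The cost is a one-sentence amendment, two data items and one table. Some suppressed recent starters would wait up to 12 weeks. Because the rule requires the same regimen, recent switchers would wait too, which slightly slows HIV-positive accrual.

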- Antidepressants: nefazodone
- Antidiuretic: conivaptan
- GI: cimetidine, aprepitant
- Hepatitis C: boceprevir, telaprevir
- Miscellaneous: Seville oranges, grapefruit, or grapefruit juice and/or pummelos, star fruit, exotic citrus fruits, or grapefruit hybrids

Strong Inducers of CYP3A4:

- Glucocorticoids: cortisone (> 50 mg), hydrocortisone (> 40 mg), prednisone (> 10 mg), methylprednisolone (> 8 mg), dexamethasone (> 1.5 mg)
- Anticonvulsants: phenytoin, carbamazepine, primidone, phenobarbital and other enzyme inducing anti-convulsant drugs (EIACD)
- Antibiotics: rifampin (rifampicin), rifabutin, rifapentine
- Miscellaneous: St. John's Wort, modafinil

Strong Inhibitors of CYP2C19:

- Antifungals: fluconazole

Strong Inducers of CYP2C19:

- Antibiotics: rifampin (rifampicin)

Lists including medications and substances known or with the potential to interact with the CYP3A or 2C19, isoenzymes are provided in [Appendix XI](#).

Drugs with KSHV antiviral activity:

- Participants receiving any medications or substances that may interfere with KSHV replication are ineligible.

Because the lists of these agents are constantly changing, it is important to regularly consult a frequently-updated list such as <http://medicine.iupui.edu/clinpharm/ddis>. Medical reference texts such as the Physicians' Desk Reference may also provide this information. Sites are encouraged to contact [name] with any questions regarding eligible ART regimens.

As part of the enrollment/informed consent procedures, the participant will be counseled on the risk of interactions with other agents, and what to do if new

medications need to be prescribed or if the participant is considering a new over-the-counter medicine or herbal product.

Lists including medications and substances known or with the potential to interfere with KSHV replication, are provided in [Appendix XII](#).

- 3.2.6 Uncontrolled intercurrent illness including, but not limited to, hepatitis C infection requiring treatment during the study, symptomatic congestive heart failure, unstable angina pectoris, cardiac arrhythmia, or psychiatric illness/social situations that in the opinion of the investigator would limit compliance with study requirements.
- 3.2.7 Pregnant women are excluded from this study because nelfinavir is a Pregnancy Category B agent that has not been studied at high doses in pregnant women. Because there is an unknown but potential risk for adverse events in nursing infants secondary to treatment of the mother with high dose nelfinavir, breastfeeding should be discontinued if the mother is treated with high dose nelfinavir.
- 3.2.8 Chronic diarrhea as defined by loose or watery stools occurring more than 3 times daily at baseline lasting more than 4 weeks or not abating on condition-appropriate therapy prior to study enrollment.
- 3.2.9 Participant is < 2 years free of another primary malignancy. Exceptions include basal cell skin cancer, Stage 0-I squamous cell cancer of the skin, cervical carcinoma in situ, anal carcinoma in situ.
- 3.2.10 Use of systemic corticosteroid therapy (except for replacement doses of glucocorticoid and/or mineralocorticoid for adrenal insufficiency). Inhaled or intranasal corticosteroids for allergic or bronchospastic conditions are permitted.

Physician Signature: _____ Date: _____

(Optional unless this section is used as an eligibility checklist)

